² If the study continues beyond Year 2 (i.e., beyond Day 778), then from Day 897 onwards, subjects will maintain evaluations for study treatment injection every 4 months with the schedule of events for those additional timepoints to alternate between the assessments done on Day 183 and those done on Day 302. Day 302 assessments would be performed at Day 897 and Day 183 assessments would be performed at Day 1016. That pattern would continue until the end of the study. Part 2 Final Follow-up Evaluation would then occur approximately 4 months after the last injection of study treatment.

³ The Part 2 Final Follow-up Evaluation will occur 4 months after the last injection of study treatment, which will either be on Day 778 or later, if Part 2 of the study continues beyond Year 2.

⁴ Subjects who terminate early will be encouraged to complete the safety evaluations scheduled for the Part 2 Early Termination Evaluation.

⁵ Inclusion/Exclusion Criteria, Informed Consent, and CSF PK must be performed on Part 2 Day 1 predose.

⁶ Vital signs include resting systolic and diastolic blood pressure, pulse rate, respiratory rate, temperature, pulse oximetry, and transcutaneous carbon dioxide. Pulse oximetry and transcutaneous carbon dioxide will be measured predose at each evaluation.

CONFIDENTIAL

The information contained herein may not be used, disclosed, or published without the written consent of Biogen MA Inc.

- ⁷ If Part 2 Day 1 study treatment injection is delayed more than 24 hours after the End of Part 1 visit, the following procedures must be done on Part 2 Day 1 predose: vital signs, weight, growth parameters, physical examination, ventilator use, neurological examination, and CSF PK. If Part 2 Day 1 study treatment injection is delayed more than 24 hours after End of Part 1 due to an AE, SAE, or other safety concern, or if Part 2 Day 1 study treatment injection is delayed more than 30 days after End of Part 1 for any reason, the following procedures must be done on Part 2 Day 1 predose: vital signs, weight, growth parameters, physical examination, ventilator use, neurological examination, ECG, CSF PK, and safety laboratory tests. Immunogenicity testing must also be repeated if Part 2 Day 1 study treatment injection is delayed more than 30 days after End of Part 1 for any reason.
- ⁸ Vital signs (resting systolic and diastolic blood pressure, pulse rate, respiratory rate, temperature, and pulse oximetry) will be collected at 4 timepoints: 1, 2, 4, and 6 hours (all ± 15 minutes) after the injection of study treatment only on Part 2 Day 1. On subsequent study days, vital signs will be collected 1 hour after the injection of study treatment.
- ⁹ Vital signs (resting systolic and diastolic blood pressure, pulse rate, respiratory rate, temperature, and pulse oximetry) will be collected on Day 2 within 20 to 24 hours after the injection of study treatment only.
- ¹⁰ At the evaluations scheduled for injection of study treatment, subjects will be assessed for the following growth parameters: body length, head circumference, chest circumference, and arm circumference. Growth parameters and weight are to be collected at the same time.
- ¹¹ Neurological examinations include assessment of mental status, level of consciousness, sensory function, motor function, cranial nerve function, and reflexes. If sedation was used, please allow sufficient recovery time for the subject to be fully engaged in the examination because it is important that the data collected truly reflect the subject's neurological performance.
- ¹² Predose and postdose.
- ¹³ ECG will be performed at Days 64, 183, 540, and 778, and at the Part 2 Final Follow-up Evaluation. ECG must be performed before obtaining blood samples for safety laboratory tests.
- ¹⁴ Blood chemistry, hematology, urinalysis, urine total protein panels, and coagulation parameters. Urine total protein and coagulation parameters will be assessed by local laboratories.
- ¹⁵ Samples for safety laboratory tests will be collected before the injection of study treatment at each dosing visit.
- ¹⁶ Blood samples for immunogenicity testing will be collected before the injection of study treatment on Days 64, 183, 302, 421, 540, 659, and 778.
- ¹⁷ Refer to [Table 7](#) for CSF PK sample schedule. The CSF samples will be analyzed for Nusinersen concentrations. The remaining CSF sample will be stored for optional future biomarker analyses.
- ¹⁸ Blood samples for PK assessment will be collected 4 hours (± 1 hour) after the injection of study treatment only on Day 1. Refer to [Table 7](#) for the plasma PK sample schedule. Plasma PK samples will be collected predose on Days 64, 183, 540, and 778.
- ¹⁹ Overnight stay (at least 24 hours) is required after the first injection of study treatment. Following all subsequent injections, a stay of at least 1 hour at the study site is required; overnight stays are optional on these days.
- ²⁰ The optional assessment of sibling SMA data collection will be performed only after obtaining consent.
- ²¹ In addition to concomitant medications, ancillary procedures will be recorded.
- ²² AEs and SAEs will be collected in the case report form from the time of signing of the informed consent form as described in [Section 15.3.1](#) and [Section 15.3.2](#).

CONFIDENTIAL

The information contained herein may not be used, disclosed, or published without the written consent of Biogen MA Inc.

Table 5 Part 1 Pharmacokinetic Sampling Schedule¹

Treatment Period	Part 1 Study Day	Timepoints	Blood Collection (mL)	CSF Collection (mL) ²
Multiple Dose: LP Injection	Day 1	Predose	NA	0.5
		4 h (\pm 1 h) postdose	0.5	NA
	Day 15	Predose	NA	0.5
	Day 29	Predose	NA	0.5
	Day 64	Predose	0.5	0.5
	Day 183	Predose	0.5	0.5
	Day 302	Predose	NA	0.5
	End of Part 1	NA	0.5	NA

CSF = cerebrospinal fluid; h = hour; min = minutes; LP = lumbar puncture; mRNA = messenger ribonucleic acid; NA = not applicable (no collection scheduled); SMA = spinal muscular atrophy.

¹ Details on sampling, preparation, and shipment are included in the Study Laboratory Manual.

² Upon consent, the collected CSF samples from the study subjects will be stored for future investigation of possible biomarkers of SMA disease (e.g., CSF mRNA, CSF protein, CSF microRNA panel), for profiling of study drug binding proteins, bioanalytical method validation purposes, stability assessments, metabolite assessments, and immunogenicity assessments (including assay development and validation purposes), or for assessing other actions of Nusinersen with plasma and CSF constituents.

Table 6 Part 2 Pharmacokinetic Sampling Schedule for Subjects Randomized to Receive Nusinersen in Part 1¹

Treatment Period	Part 2 Study Day	Timepoints	Blood Collection (mL)	CSF Collection (mL) ²
Multiple Dose: LP Injection	Day 1	Predose	NA	0.5
		4 h (\pm 1 h) postdose	0.5	NA
	Day 120	Predose	NA	0.5
	Day 239	Predose	0.5	0.5
	Day 358	Predose	NA	0.5
	Day 477	Predose	0.5	0.5
	Day 596	Predose	NA	0.5
	Day 715	Predose	0.5	0.5
	Part 2 Final Follow-Up	NA	0.5	NA

CSF = cerebrospinal fluid; h = hour; min = minutes; LP = lumbar puncture; mRNA = messenger ribonucleic acid; NA = not applicable (no collection scheduled); SMA = spinal muscular atrophy.

CONFIDENTIAL

The information contained herein may not be used, disclosed, or published without the written consent of Biogen MA Inc.

¹ Details on sampling, preparation, and shipment are included in the Study Laboratory Manual.

² Upon consent, the collected CSF samples from the study subjects will be stored for future investigation of possible biomarkers of SMA disease (e.g., CSF mRNA, CSF protein, CSF microRNA panel), for profiling of study drug binding proteins, bioanalytical method validation purposes, stability assessments, metabolite assessments, and immunogenicity assessments (including assay development and validation purposes), or for assessing other actions of Nusinersen with plasma and CSF constituents.

Table 7 Part 2 Pharmacokinetic Sampling Schedule for Subjects Randomized to Receive Sham Procedure in Part 1¹

Treatment Period	Part 2 Study Day	Timepoints	Blood Collection (mL)	CSF Collection (mL) ²
Multiple Dose: LP Injection	Day 1	Predose	NA	0.5
		4 h (±1 h) postdose	0.5	NA
	Day 15	Predose	NA	0.5
	Day 29	Predose	NA	0.5
	Day 64	Predose	0.5	0.5
	Day 183	Predose	0.5	0.5
	Day 302	Predose	NA	0.5
	Day 421	Predose	NA	0.5
	Day 540	Predose	0.5	0.5
	Day 659	Predose	NA	0.5
	Day 778	Predose	0.5	0.5
	Part 2 Final Follow-Up	NA	0.5	NA

CSF = cerebrospinal fluid; h = hour; min = minutes; LP = lumbar puncture; mRNA = messenger ribonucleic acid; NA = not applicable (no collection scheduled); SMA = spinal muscular atrophy.

¹ Details on sampling, preparation, and shipment are included in the Study Laboratory Manual.

² Upon consent, the collected CSF samples from the study subjects will be stored for future investigation of possible biomarkers of SMA disease (e.g., CSF mRNA, CSF protein, CSF microRNA panel), for profiling of study drug binding proteins, bioanalytical method validation purposes, stability assessments, metabolite assessments, and immunogenicity assessments (including assay development and validation purposes), or for assessing other actions of Nusinersen with plasma and CSF constituents.

CONFIDENTIAL

The information contained herein may not be used, disclosed, or published without the written consent of Biogen MA Inc.

[figure not shown]

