		Predose ⁵	LP	Postdose		Predose	LP	Postdose		
Informed Consent	X ⁵									
Inclusion/ Exclusion Criteria	X ⁵									
Vital Signs ⁶	X ⁷		X ⁸		X		X ⁸		X	
Weight	X ⁷				X				X	
Growth Parameters ⁹	X ⁷				X				X	
Physical Examination	X ⁷				X				X	
Ventilator Use	X ⁷			X	X			X	X	
Neurological Examination ¹⁰	X ^{7,11}		X ¹¹		X ¹¹		X ¹¹		X	
ECG	X ⁷				X ¹²				X ¹²	
Safety Laboratory Tests ¹³	X ⁷				X ¹⁴				X	
Immunogenicity Sample	X ⁷				X ¹⁵				X	
CSF PK ¹⁶	X ^{5,7}				X					
Plasma PK ¹⁷			X ¹⁷		X ¹⁷				X	
Study Treatment Injection		X				X				
Telephone Contact for Safety Monitoring (+3 Days)				X				X		
HINE and WHO Motor Milestone					X				X	
Clinical Global Impression of Change					X				X	

CONFIDENTIAL

The information contained herein may not be used, disclosed, or published without the written consent of Biogen MA Inc.

Study Period	Part 2 Treatment/Follow-Up							
	Day 1			Day 2 ¹	Days 120, 239, 358, 477, 596, 715 (± 7 days) ²			Days 121, 240, 359, 478, 597, 716 ¹
Study Day	Predose ⁵	LP	Postdose		Predose	LP	Postdose	
and ACEND								
Optional Sibling SMA Data Collection ¹⁸	X							X
Con Med Recording ¹⁹	X-----X							
Adverse Event Collection ²⁰	X-----X							

ACEND = Assessment of Caregiver Experience with Neuromuscular Disease; AE = adverse event; Bi-PAP = bilevel positive airway pressure; Con Med = concomitant medication; CSF = cerebrospinal fluid; ECG = electrocardiogram; HINE = Hammersmith Infant Neurological Examination; LP = lumbar puncture; PK = pharmacokinetic(s); SAE = serious adverse event; WHO = World Health Organization.

¹ There will be safety monitoring through telephone contact on the day following the injection of study treatment (i.e., Days 2, 121, 240, 359, 478, 597, and 716). During that telephone contact, changes in concomitant medications and AEs, information on the subject’s daily ventilator/Bi-PAP use, and health status will be recorded.

² If the study continues beyond Year 2 (i.e., beyond Day 715), then from Day 835 onwards, subjects will maintain evaluations for study treatment injection every 4 months with the assessments for those additional timepoints to alternate between the assessments done on Day 120 and those done on Day 239. Day 120 assessments would be performed at Day 835 and Day 239 assessments would be performed at Day 954. The alternating pattern would continue until the end of the study. Part 2 Final Follow-up Evaluation would then occur approximately 4 months after the last injection of study treatment.

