³ The Part 2 Final Follow-up Evaluation will occur 4 months after the last injection of study treatment, which will either be on Day 716 or later, if Part 2 of the study continues beyond Year 2.

⁴ Subjects who terminate early will be encouraged to complete the safety evaluations scheduled for the Part 2 Early Termination Evaluation.

⁵ Inclusion/Exclusion Criteria, Informed Consent, and CSF PK must be performed on Part 2 Day 1.

⁶ Vital signs include resting systolic and diastolic blood pressure, pulse rate, respiratory rate, temperature, pulse oximetry, and transcutaneous carbon dioxide. Pulse oximetry and transcutaneous carbon dioxide will be measured predose at each evaluation.

⁷ If Part 2 Day 1 study treatment injection is delayed more than 24 hours after the End of Part 1 visit, the following procedures must be done on Part 2 Day 1 predose: vital signs, weight, growth parameters, physical examination, ventilator use, neurological examination, and CSF PK. If Part 2 Day 1 study treatment injection is delayed more than 24 hours after End of Part 1 due to an AE, SAE, or other safety concern, or if Part 2 Day 1 study treatment injection is delayed more than 30 days after End of Part 1 for any reason, the following procedures must be done on Part 2 Day 1 predose: vital signs, weight, growth parameters, physical examination, ventilator use, neurological examination, ECG, CSF PK, and safety laboratory tests. Immunogenicity testing must also be repeated predose if Part 2 Day 1 study treatment injection is delayed more than 30 days after End of Part 1 for any reason.

⁸ Vital signs (resting systolic and diastolic blood pressure, pulse rate, respiratory rate, temperature, and pulse oximetry) will be collected 1 hour (± 15 minutes) after the injection of study treatment.

⁹ At the evaluations scheduled for injection of study treatment, subjects will be assessed for the following growth parameters: body length, head circumference, chest circumference, and arm circumference. Growth parameters and weight are to be collected at the same time.

¹⁰ Neurological examinations include assessment of mental status, level of consciousness, sensory function, motor function, cranial nerve function, and reflexes. If sedation was used, please allow sufficient recovery time for the subject to be fully engaged in the examination because it is important that the data collected truly reflect the subject’s neurological performance.

CONFIDENTIAL

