7.2.2. Treatment

Part 1

Eligible subjects will be admitted to the study site on Part 1 Day 1, undergo predose evaluations, and then receive an LP injection of Nusinersen or a sham procedure. After the injection on Day 1, subjects will remain at the study site for at least 24 hours after the procedure for safety monitoring.

Subjects will return to the study site on Days 15, 29, 64, 183, and 302 (± 1 day for Days 15 and 29 and ± 7 days for all other days) for follow-up evaluations and subsequent injections of study treatment or sham procedure, for a total of 6 injections or sham procedures over a dosing period of 10 months. During these 5 evaluations, all subjects will remain at the study site for at least 6 hours postdose for safety monitoring. An overnight stay is optional, at the discretion of the Investigator. Safety monitoring by telephone contact will occur on the day after injection of study treatment or sham procedure. In addition, the study site will monitor the subject's condition through telephone contact every other week (excluding weeks with study visit) throughout the study period.

After completing the End of Part 1 Evaluation assessments, all eligible subjects may elect to enroll in Part 2.

Based on emergent data from the Nusinersen clinical development program, the Sponsor may decide to terminate Part 1 early, and all subjects may be offered the opportunity to transition to Part 2 prior to completion of all Part 1 Evaluation assessments. All subjects enrolled in the study at the time of Sponsor termination will be considered Part 1 completers. The next study evaluation for those subjects will serve as an End of Part 1 Evaluation, which may occur at any time prior to the next scheduled Part 1 study evaluation.

Unblinding will occur in order for the subjects to transition from Part 1 to Part 2.

End of Part 1 Evaluation assessments are required to be done prior to the transition to Part 2. After performing the End of Part 1 Evaluation assessments, the subject may immediately transition to Part 2.

Part 2

Part 2 study procedures and schedules will be determined based on the subject's treatment assignment in Part 1.

CONFIDENTIAL

The information contained herein may not be used, disclosed, or published without the written consent of Biogen MA Inc.

Subjects who were randomized to receive Nusinersen in Part 1

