End of Part 1 Evaluation assessments will be used to determine subject eligibility for Part 2 of the study. For subjects who were receiving Nusinersen in Part 1, Part 2 Day 1 will occur following the End of Part 1 Evaluation or approximately 4 months following the last injection of Nusinersen in Part 1. On Part 2 Day 1, these subjects will undergo predose evaluations according to the schedule of events ([Table 3](#)) and then receive their first dose of Nusinersen for Part 2 (next maintenance dose).

Subjects will return to the study site on Days 120, 239, 358, 477, 596, and 715 (± 7 days for all days) for follow-up evaluations and subsequent injections of Nusinersen over a dosing period of approximately 24 months. Subjects will remain at the study site for at least 1 hour postdose for safety monitoring and can be discharged at the discretion of the site Investigator and in compliance with the institutional requirements once the subjects have adequately recovered from the dosing procedure. An overnight stay is optional, at the discretion of the Investigator. Safety monitoring by telephone contact will occur on the day after injection of study treatment. In addition, the study site will monitor the subject's condition through telephone contact every other week (excluding weeks with study visit) throughout the study period.

Subjects who were randomized to receive sham procedure in Part 1

End of Part 1 Evaluation assessments will be used to determine subject eligibility for Part 2 of the study. For subjects who were receiving sham procedure in Part 1, Part 2 Day 1 will occur following the End of Part 1 Evaluation or as soon as possible following their End of Part 1 Evaluation, in the event of early termination by the Sponsor due to emergent data from the Nusinersen clinical development program. On Part 2 Day 1, these subjects will undergo predose evaluations according to the schedule of events ([Table 4](#)) and then receive their first injection of Nusinersen (first loading dose). Subjects will remain at the study site for at least 24 hours after the procedure for safety monitoring.

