#### Missing data

##### *Part 2 analysis*

For Part 2 HINE motor milestones, Baseline will be retrieved from Part 1 and it will be the last assessment in Part 1.

Some general rules for the approaches to imputation of missing data are described in the following sections.

- 1) If a subject has any milestones missing at baseline then the missing milestone will be imputed using the median baseline value within the age of SMA onset ( $\leq 6$  months,  $>6$  months). for the correspondent milestone level
- 2) If a subject has any missing milestones at any visit that is not last visit, then the missing milestone will be imputed using a linear interpolation at the milestone level for any actual scheduled study visits.
- 3) If a subject has any missing milestones at last visit, then the missing milestone will be imputed using the lowest observed value for milestone assigned within the age of SMA onset ( $\leq 6$  months,  $>6$  months) and group to which the subject belongs at that visit (e.g., if a previous control subject's last visit is Day 120, then the at lowest observed value for the previous control group at Day 120 is used for the non-missing values for the specific motor milestone).

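### When the first Part 2 dose is delayed, growth and ventilator use are measured again but HINE is not, and the SAP sets no age limit on the Part 2 HINE baseline

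*Protocol*

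**What the plan says.** **Schedule.** In protocol Tables 3 and 4 (section 4.2.2) the row "HINE and WHO Motor Milestone" is blank on Part 2 Day 1. Its first entry is Day 120 for children previously on nusinersen and Day 64 for children previously on sham. Table 2 has HINE at the End of Part 1 visit.

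**Repeat rule.** Footnote 7 of Tables 3 and 4 has two tiers. After a delay of more than 24 hours the predose repeats are "vital signs, weight, growth parameters, physical examination, ventilator use, neurological examination, and CSF PK". The second tier applies when a safety problem holds the dose back by more than 24 hours, and also when "Part 2 Day 1 study treatment injection is delayed more than 30 days after End of Part 1 for any reason"; its list is "vital signs, weight, growth parameters, physical examination, ventilator use, neurological examination, ECG, CSF PK, and safety laboratory tests". Table 4 adds: "Immunogenicity testing must also be repeated if Part 2 Day 1 study treatment injection is delayed more than 30 days after End of Part 1"; Table 3 has the same rule. HINE is in neither tier, and no maximum delay is stated.

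**Baseline rule.** SAP 4.5.1 states: "For Part 2 HINE motor milestones, Baseline will be retrieved from Part 1 and it will be the last assessment in Part 1". HINE response and HINE change from baseline are both Part 2 outputs in that section.

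**Timing.** If the sponsor stops Part 1 early, protocol 7.2.2 lets the End of Part 1 Evaluation fall at a time "which may occur at any time prior to the next scheduled Part 1 study evaluation". A child on nusinersen then starts Part 2 after that evaluation "or approximately 4 months following the last injection of Nusinersen in Part 1". A child on sham starts as soon as possible after it.

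**The concern.** Three efficacy measures have a Part 1 baseline value to carry forward: ventilator use, growth and HINE. Footnote 7 renews the first two after a delay and leaves the third. (WHO milestones and ACEND are not assessed in Part 1, and the global impression is itself a change score.) The general neurological examination is repeated, but it does not score HINE Section 2.

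Any motor change between the End of Part 1 HINE and the first Part 2 dose is therefore booked to Part 2. For a former-sham child that period is untreated, so loss or gain in it is read as change on nusinersen. This reaches the Part 2-only HINE tables and the integrated column for previous controls in Part 2, which SAP section 2 sets beside the same children's sham period. The Part 1 HINE baseline is taken predose on Day 1, so the two columns can rest on baselines of different age.

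**Working it through.** The plan gives no figure to reproduce. The check is day arithmetic on scheduled visits.

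**Step 1: nominal first HINE interval in Part 2.** Former nusinersen: Day 120 − Day 1 = 119 days. Former sham: Day 64 − Day 1 = 63 days.

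**Step 2: effect of a gap.** Let g be the days from the last Part 1 HINE to the first Part 2 dose. Interval spanned = nominal + g; stretch = g / nominal.

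| g (days) | Former sham | Former nusinersen |
|---|---|---|
| 0 | 63 | 119 |
| 30 | 93 (30/63 = +48%) | 149 (30/119 = +25%) |
| 60 | 123 (+95%) | 179 (+50%) |
| 90 | 153 (+143%) | 209 (+76%) |
| 119 | no scheduled route | 238 (+100%) |

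**Step 3: how large g can be.** For nusinersen, dosing intervals are 183 − 64 = 119 and 302 − 183 = 119 days. If the End of Part 1 visit is held just after an injection and Part 2 Day 1 waits until about 4 months after it, g approaches 119 days. A former-sham child has no dosing interval to wait out, so g exceeds a few days only through an incidental delay such as illness. Footnote 7 itself provides for delays of more than 30 days.

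**Step 4: which tables are exposed.** Under SAP section 2, the integrated nusinersen column runs from the first Part 1 dose, so g does not enter it. The integrated column for previous controls in Part 2 starts at the first nusinersen dose. With no HINE on that day, its baseline must come from Part 1. SAP 4.1 labels every study day up to 1 as baseline, with no lower limit. Both groups are exposed in the Part 2-only tables.

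**Step 5: size in points.** The documents give no HINE drift rate. As an assumption only, take −0.5 to +0.5 points per month of 30.44 days. Drift = rate × g / 30.44, which is about ±0.5 points at 30 days, ±1.0 at 60 and ±1.95 at 119. SAP 4.5.1 lets a 1-point gain in one of six categories make a responder if improvements outnumber worsenings. The same section also defines improvement as a 2-point rise in total score, so the threshold is not settled.

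**Step 6: weight of one child.** At most 7 previous controls: 1/7 = 14.3 percentage points. At most 14 previous-nusinersen children: 1/14 = 7.1. These are the weights of any one child, not estimates of bias.

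**The case against.** The documents point towards short gaps. Protocol 7.2.2 allows immediate transition. Protocol 9.3 unblinds site staff early so that sham children come in quickly and nusinersen children keep their dosing interval. Table 2 footnote 14 allows local laboratory tests at End of Part 1 to fit in the Part 2 Day 1 dose. The SAP was written after Part 1 stopped. Its section 1.3 places the follow-up visit about 4 months after the last Part 1 dose, and section 2 says nusinersen children moved over on their own dose schedule. Both put HINE near the next dose. HINE is exploratory, Part 2 has no formal statistical analysis, and most of the repeated items suit a safety recheck before dosing. All of this stands. It limits the likely size but does not give a delayed child a current HINE baseline.

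A reader might infer more than the text supports:

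- **That nearly every baseline measure except HINE is renewed.** This fits only the second tier. For a non-safety delay of between 24 hours and 30 days, ECG, laboratory tests and immunogenicity are not repeated either.
- **That the sham-to-nusinersen comparison rests on baselines up to 119 days old.** The route to 119 days exists only for nusinersen children, and their integrated column is unaffected.
- **That the gap causes benefit from Part 1 dosing to be counted as Part 2 gain.** That happens with no gap at all: protocol 5.5 gives a half-life of 4 to 6 months, and SAP 3.3 treats children as exposed from first dose to last follow-up.

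**Conclusion.** The omission is real, and its reach is narrow. It concerns delayed children only, in exploratory, descriptive HINE summaries. It matters most for a delayed former-sham child, whose untreated change enters the Part 2-only tables and the integrated column for previous controls in Part 2. At a 30-day gap that child's first HINE interval is about half as long again as planned. The direction of any bias depends on the child's natural course. For former-nusinersen children the exposure is confined to the Part 2-only tables, and 119 days is a ceiling rather than an expectation.

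The conclusion assumes that at least one child had a material delay, which the documents neither show nor rule out. It also assumes that delay is counted from the End of Part 1 visit. Table 2 footnote 4 dates End of Part 1, for children who continue, as the day of the first Part 2 dose. Read literally, that makes the second-tier delay zero for everyone, so the two footnotes need reconciling. The point is a cheap improvement, not a threat to the trial's primary safety objective.

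**What to change.** **In the SAP (the operative change, since Part 1 has stopped and eligible children are already in Part 2).** In 4.5.1, add a listing, per child, of days from the HINE baseline to the first Part 2 dose. Repeat the Part 2 HINE change and responder summaries, and the integrated column for previous controls in Part 2, without children whose baseline is more than 30 days old. The listing also shows shorter gaps, which the 30-day cut leaves in. Cost: one listing and one sensitivity summary from dates already collected.

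**For any Part 2 Day 1 visit still to come.** Add HINE Section 2 to the second-tier list in footnote 7 of protocol Tables 3 and 4 and of the SAP copies, and name that predose value as the Part 2 HINE baseline in SAP 4.5.1. Cost: one non-invasive examination by the existing assessor at a visit the child already attends. Superseded protocol version 2 marked HINE on that day, which suggests it is feasible.

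**Wording.** Reconcile Table 2 footnote 4 with footnote 7 so that the date from which delay is counted is unambiguous.
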